# 2.7.2 Deaths

Should any deaths be recorded, these will be listed

# 2.7.3 Laboratory data

Abnormal laboratory results that meet the criteria for adverse events will be summarized as part of the AE reporting.

# 2.12 Interim analysis

An interim analysis of the core study was performed with database lock in May 2020 based on approximately 187 patients who had completed to week 16 or discontinued the study. This IA

Novartis	For business use only	Page 29
SAP		CZPL389A2203

was planned to support decision making concerning future trials in the ZPL389 development program and focused on efficacy in terms of IGA response, EASI and pruritus. It was not the intention to stop the trial. The interim analysis charter described the steps takes to restrict the knowledge of the results of the study so as not to bias the trial conduct post interim analysis. Once the results were seen, the decision made to stop the core and extension studies.

# 3 Sample size calculation

The planned sample size for the core study was 360 subjects. Since the study was stopped early the final sample size will be less than this.

The sample size was determined with the software ADDPLAN DF, version 3.1.8, with settings for minimum power function and model based contrasts.

The sample size was derived to detect a dose-response with 90% power and a one-sided alpha of 2.5%. A placebo response rate of 10% was assumed. A maximum treatment effect for ZPL389 of 20%-points higher than placebo wass assumed. An unbalanced allocation ratio of 2:1:1:2:2 corresponding to treatment arms placebo: 3 mg: 10 mg: 30 mg: 50 mg, with more subjects allocated to placebo and the higher doses, was chosen to increase the precision of the estimate for the treatment effect at doses in the expected efficacious dose range.

Under these assumptions, a sample size of 360 subjects in total will be required, randomized to 90:45:45:90:90 subjects corresponding to placebo: 3 mg: 10 mg: 30 mg: 50 mg treatment arms.

# 4 Change to protocol specified analyses

A change was made to the primary estimand regarding adjuidcation of confounding medication use. This change was made following the interim analysis where it was established that handling use of confounding medication did not affect the overall conclusions and so it was decided not to perform the adjudication.

Following the interim analysis results which showed no treatment effect of ZPL389 on efficacy and the subsequent early stopping of the trial, the dose-response analysis using MCP-Mod methods as described in the protocol will not be performed.

# 5 Appendix

# 5.1 Imputation rules

## 5.1.1 Study drug

Any partial dates will be imputed as follows:

Take the earlier day of

- The last day in the month and
- The end day of the corresponding epoch.

#### 5.1.2 Concomitant medication date imputation

Impute concomitant medication (CM) end date:

1. If CM end day is missing and CM month/year are non-missing then impute CM day as the minimum of treatment end date and the last day of the month.

2. If CM end day/month are missing and CM year is non-missing then impute CM day as the minimum of treatment end date and the end of the year (31DECYYYY).

3. If imputed CM end date is less than the CM start date, use the CM start date as the imputed CM end date.

Impute CM start date:

1. If the CM start date year value is missing, the imputed CM start date is set to one day prior to treatment start date.

2. If the CM start date year value is less than the treatment start date year value, the CM started before treatment. Therefore:

a. If the CM month is missing, the imputed CM start date is set to the mid-year point (01JulYYYY).

b. Else if the CM month is not missing, the imputed CM start date is set to the midmonth point (15MONYYY).

3. If the CM start date year value is greater than the treatment start date year value, the CM started after treatment. Therefore:

a. If the CM month is missing, the imputed CM start date is set to the year start point (01JanYYYY).

b. Else if the CM month is not missing, the imputed CM start date is set to the month start point (01MONYYY).

4. If the CM start date year value is equal to the treatment start date year value:

a. And the CM month is missing or the CM month is equal to the treatment start date month, then the imputed CM start date is set to one day prior treatment start date.

b. Else if the CM month is less than the treatment start date month, the imputed CM start date is set to the mid-month point (15MONYYY).

c. Else if the CM month is greater than the treatment start date month, the imputed CM start date is set to the month start point (01MONYYYY).

If complete (imputed) CM end date is available and the imputed CM start date is greater than the (imputed) CM end date, then imputed CM start date should be set to the (imputed) CM end date.

#### 5.1.3 Prior therapies date imputation

See Section 5.1.2.

# 5.1.4 Post therapies date imputation

See Section 5.1.2.

# 5.1.5 First diagnosis date imputation

1. If first diagnosis date is complete then imputed first diagnosis date = first diagnosis date.

2. If only year is present in the first diagnosis date then do the following:

a. If the year part of the first diagnosis date is equal to the year part of the inform consent date then imputed first diagnosis date = Jan 1 of the year of the first diagnosis date

b. Otherwise imputed first diagnosis date = Jul 1 of the year of the first diagnosis date

3. If only month and year part are present in the first diagnosis date then do the following:

a. If the month and year part of the first diagnosis date is equal to the month and year part of the inform consent date then imputed first diagnosis date = 1st of the month of the year of the first diagnosis date

b. Otherwise imputed first diagnosis date = 15th of the month of the year of the first diagnosis date.

# 5.2 Statistical models

# 5.2.1 Analysis of continuous data

## Mixed model repeated measures (MMRM)

Continuous variables analyzed via mixed model repeated measures (MMRM) assume that data are missing at random (MAR) assumption.

Treatment group, visit, baseline IGA and geographical region will be fitted as factors and baseline values will be fitted as continuous covariates. Treatment group by visit and visit by baseline value will be included as interaction terms in the model. A term for visit will be included in the repeated statement (in SAS PROC MIXED or PROC GLM) and an unstructured covariance matrix will be used thus allowing adjustment for correlations between time points within patients. The denominator degrees of freedom will be calculated using the Kenward-Roger method.

The model described above allows the relationship to baseline to vary for each visit, but assumes that the effects of baseline IGA and geographical region will remain constant over all visits. From this analysis, the adjusted means for each treatment group and at each timepointt, the difference between the adjusted means (ZPL389 groups vs placebo) at each timepoint, 95% confidence interval around these differences.

SAS code for mixed model: proc mixed data=aaa; class TRT USUBJID AVISITN IGA BASELINE GEOGRAPHY; model CHG=TRT AVISITN IGA\_BASELINE GEOGRAPHY BASE TRT\*AVISITN BASE\*AVISITN / s ddfm=kr;

lsmeans TRT\*AVISITN / diff cl; repeated AVISITN / type=un subject=USUBJID; run;

In case the MMRM model does not converge the following sequential steps will be used:

- 1. change ddfm=kr to ddfm=bw. If still no convergence, perform step 2.
- 2. change type=un to type=cs. If still no convergence, perform step 3.
- 3. remove covariates in the following order until convergence: GEOGRAPHY, BASE\*AVISITN.

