# 2.6.7 Statistical hypothesis, model, and method of analysis

For all estimands based on binary response rates (e.g. IGA response, EASI50 response, EASI75 response) the simple response rates for each treatment group will be calculated (i.e. number of responders (after imputation as necessary) / the number of subjects in that treatment group.

Differences in response rates between ZPL389 dose groups and placebo will be calculated, and the respective 95% confidence intervals derived using a normal approximation.

For estimands based on continuous data (e.g. percentage change from baseline in EASI, approach will be used. The model will contain treatment group, baseline EASI score, geographical region if possible, baseline IGA score, visit, baseline value\*visit and treatment group\*visit as covariates, and will use an unstructured covariance matrix. Estimates of the mean responses for each visit and treatment group, and of the differences between treatment groups at week 16 will be obtained from this model, together with 95% confience intervals.

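### The MMRM non-convergence sequence opens with a step that cannot affect convergence and then goes straight to homogeneous compound symmetry with model-based errors, which can miscalibrate the Week 16 EASI intervals if the unstructured fit fails

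*SAP*

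**What the plan says.** SAP 5.2.1 (Mixed model repeated measures) gives the repeated statement as "repeated AVISITN / type=un subject=USUBJID; run" and adds: "The denominator degrees of freedom will be calculated using the Kenward-Roger method". If the model does not converge, three steps follow in order:

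1. The degrees-of-freedom option switches from Kenward-Roger to between-within; nothing else in the model is altered.
2. The covariance structure is then replaced: "change type=un to type=cs. If still no convergence, perform step 3".
3. Terms leave the mean model one at a time, region first and the baseline-by-visit interaction second.

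The procedure call in the SAP code has no EMPIRICAL option and no step adds one, so standard errors stay model-based throughout. No structure between unstructured and compound symmetry is listed.

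SAP 2.6.7 says that estimates "of the differences between treatment groups at week 16 will be obtained from this model", with 95% confidence intervals. Protocol 9.5.1 specifies the unstructured covariance for the same endpoint and gives no fallback.

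**The concern.** A fallback sequence should give up as little as possible at each step. This one does not.

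- Step 1 cannot help the optimisation. It only gives up the Kenward-Roger adjustment, and because the steps are cumulative, any later fit also runs without it.
- Step 2 moves from the most flexible covariance to one that forces a single variance and a single correlation on all visits. If the Week 16 variance differs from the average over visits, the model-based standard error at Week 16 is wrong.
- The order sits oddly with SAP 2.6.7, which includes geographical region only where feasible. The covariance is given up at step 2, while that optional covariate survives until step 3.

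At stake is the calibration of the Week 16 interval for percent change in EASI, a secondary endpoint that SAP Table 1-1 keeps in the report. SAP 2.6.2 sets EASI data to missing after confounding medication or any treatment discontinuation. With incomplete data, the assumed covariance affects the estimates as well as their standard errors.

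**Working it through.** **Benchmark.** No figure in the plan depends on the fallback, so there is none to reproduce. The benchmark is the stated level: "95% confidence interval around these differences".

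**Step 1.** REML maximises an objective in the covariance parameters. The denominator degrees of freedom are worked out afterwards from the fitted model. Changing kr to bw leaves the objective and its maximisation unchanged.

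**How likely is failure of the unstructured fit?** Protocol Table 6-1 has six post-baseline visits up to Week 16 (Weeks 2, 4, 6, 8, 12 and 16), which gives 6×7/2 = 21 covariance parameters. About 187 subjects were already in the interim analysis (SAP 2.12). Failure is not expected. SAP Table 2-1 has 17 post-baseline windows when the extension is included; if all entered one model there would be 17×18/2 = 153 parameters. The SAP does not state which visits enter.

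**Step 2, complete data.** With treatment-by-visit means and no missing data, compound symmetry uses the average visit variance at every visit:

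- ratio r = SE(model)/SE(true) = √(mean visit variance) / SD at Week 16
- coverage = 2Φ(1.96·r) − 1

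The documents give no SD, variance profile or correlation for EASI. The SDs below, in percentage points and linear over six visits, are assumptions.

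- 25 to 35: visit SDs 25, 27, 29, 31, 33, 35; mean variance 5470/6 = 911.7; r = 30.19/35 = 0.86; coverage 91%.
- 25 to 45: mean variance 7630/6 = 1271.7; r = 35.66/45 = 0.79; coverage 88%.
- 20 to 40: mean variance 5680/6 = 946.7; r = 30.77/40 = 0.77; coverage 87%.
- Flat 35: r = 1; coverage 95%.
- 40 to 30: mean variance 7420/6 = 1236.7; r = 35.17/30 = 1.17; coverage 98%.

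**Step 2, with dropout.** Large-sample calculation with monotone dropout of 0, 20 or 35% (completely at random) and three correlation patterns (constant 0.6; serial decay of 0.85 or 0.93 per two weeks). Compound-symmetry parameters are the best-fitting ones; the true SE comes from the sandwich form A⁻¹BA⁻¹.

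| Assumed SD, Week 2 to 16 | SE(model)/SE(true) | Coverage of nominal 95% |
|---|---|---|
| Rising 30 to 40 | 0.81–0.88 | 88.8–91.5% |
| Rising 25 to 45 | 0.73–0.79 | 84.6–88.0% |
| Rising 20 to 50 | 0.66–0.73 | 80.6–84.7% |
| Flat 35 | 0.92–1.00 | 92.9–95.0% |
| Falling 40 to 30 | 1.07–1.19 | 96.3–98.0% |

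Flat SD gives exactly 95% with complete data, or when the true correlation really is constant.

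**Simulation check.** N = 187 at 2:1:1:2:2, about 25% dropout at random given the observed data, decaying correlation, 600 runs (Monte Carlo SE about 0.9 points near 95%). Compound symmetry covered 95.3% (flat), 85.7% (25 to 45; mean SE 7.54 against an empirical SD of 9.97) and 98.2% (40 to 30). The unstructured fit covered 96.0% in each.

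**The remedy.** Same design, 250 runs, Monte Carlo SE about 1.5 to 2.5 points:

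| Assumed SD | Compound symmetry, model-based | Compound symmetry, sandwich |
|---|---|---|
| 25 to 35 | 86.4% | 94.0% |
| 25 to 45 | 84.0% | 95.2% |
| Flat 35 | 93.6% | 94.4% |

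**The case against.** The strongest reply is that this is a contingency that will probably never run. Twenty-one covariance parameters, pooled over arms, should be estimable with 187 or more subjects. SAP 2.6.5 (up to Week 16) and 2.6.6 (after Week 16) treat the two periods separately, which points to a model on core visits only. The trial was stopped for lack of efficacy, MCP-Mod was dropped, and the SAP ties no dose decision to the EASI interval. All of this stands and keeps the point small.

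A reader might infer that the plan gives Week 16 intervals that are too narrow. The documents do not support that. The unstructured fit must first fail, and then the direction depends on the variance profile, which neither document gives. Rising spread is plausible: percent change is zero for everyone at baseline, and Protocol 3.3 says that the drug's effect had not levelled off by eight weeks in the earlier study. But that concerns mean response, not variance at Week 16 relative to earlier visits. A falling profile makes the intervals too wide.

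A reader might also call this a key secondary endpoint. The protocol and SAP list it only as secondary; there is no key tier.

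Step 1 does little direct harm, since step 2 follows if it achieves nothing. That is fair, but it is still no remedy for the problem it is listed against. Finally, the sandwich corrects the standard error only. Under dropout at random, a wrong covariance can also bias the estimate. That stands, and it is why better-fitting structures should be tried first.

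**Conclusion.** The point holds in conditional form. From the text alone, step 1 cannot affect convergence, and step 2 goes directly to homogeneous compound symmetry with model-based errors. If the unstructured fit fails, nominal 95% coverage at Week 16 becomes about 85 to 91% for moderately rising SDs (lower for a steeper rise), about 93 to 95% for a flat SD, and about 96 to 98% for a falling one. These figures rest on assumed SD profiles, correlations and dropout. The likelihood of reaching step 2 is low with core visits only and higher if extension visits share the model. Nothing changes if the unstructured model converges, and no stated conclusion of the trial depends on it. It is a cheap improvement, not a necessary correction.

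**What to change.** Replace the sequence in SAP 5.2.1 with the following:

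1. Delete the change from kr to bw as a convergence remedy.
2. If the unstructured fit fails, try heterogeneous structures in a fixed order, for example TOEPH, then ARH(1), then CSH, keeping Kenward-Roger. The order is a judgement; what matters is that it is fixed in advance and lets the variance differ by visit.
3. Only if these fail, use plain CS with the EMPIRICAL option and ddfm=bw.
4. Keep covariate removal as the last step.

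It would also help to state that the Week 16 model uses the six core post-baseline visits, if that is the intention, since this settles how likely the fallback is.

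The cost is a few code options in a contingency. The downside is a longer fallback list to program and validate.

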## 5.2.2 Analysis of binary data

#### Risk difference and 100\*(1-α)% confidence interval

For an investigational drug group with  $n_1$  subjects at risk, independent from the control group (e.g., placebo or comparator) with  $n_0$  subjects at risk, of whom  $x_1$  and  $x_0$  experience a certain event, the risk difference is estimated as  $p_1$ - $p_0$  with  $p_1 = x_1/n_1$  and  $p_0 = x_0/n_0$ .

Exact unconditional confidence limits for the risk difference will be obtained with SAS procedure PROC FREQ and option RISKDIFF in the TABLES statement, specifying the RISKDIFF option also in the EXACT statement.

#### Logistic regression

Where logistic regression is specified, the binary outcome variable will be evaluated using a logistic regression model with treatment regimen, baseline IGA, geographical region (if possible).

All p-values reported on linear hypotheses about regression coefficients will be based on the Wald tests from Type III analyses. In the SAS procedure PROC GENMOD, a Type III analysis will be performed by adding the model options: TYPE3, DIST=BIN, and LINK=LOGIT. Logistic regression will be applied to response variables at each visit, and the following steps will be performed:

- 1. Run the PROC GENMOD procedure;
- 2. If convergence not reached, remove the covariates from the model one by one until convergence is reached; start with removing region, followed by baseline IGA;
- 3. If convergence not reached, perform Fisher's exact test.

It should be noted that this model might not converge if response rates are too low.

SAS code for logistic regression:

proc logistic data=aaa;

class TRT STRATA / param=glm;

Model AVAL (event='1') = TRT WEIGHT STRATA;

LSMEANS TRT / diff cl exp ilink;

run;

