# 2 Statistical methods

# 2.1 Data analysis general information

Novartis will perform the analyses for this study. Statistical software SAS verion 9.4 or later will be used.

All available data from the core and extension studies will be presented together.

Where summary statistics are presented these will include, for continuous variables N, mean, standard deviation, minimum, and maximum, and for discrete variables, counts and appropriate percentages.

If not otherwise specified, p-values will be presented for two-sided hypothesis testing, twosided confidence intervals will be displayed and the level of significance will be set to 5% twosided.

In general listings will be presented by treatment sequence showing the sequence of treatments in the core and extension study, i.e as follows and in this order

- Placebo did not participate in extension
- Placebo ZPL389 50mg
- Placebo ZPL389 30mg

- ZPL389 3mg did not participate in extension
- ZPL389 3mg ZPL389 30mg
- ZPL389 3mg ZPL389 50mg
- ZPL389 10mg did not participate in extension
- ZPL389 10mg ZPL389 30mg
- ZPL389 10 mg ZPL389 50mg
- ZPL389 30mg did not participate in extension
- ZPL389 30mg ZPL389 30mg
- ZPL389 50mg did not participate in extension
- ZPL389 50mg ZPL389 50mg

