# 2.5.2 Statistical hypothesis, model, and method of analysis

The key questions to address this objective are

- Is there a dose-response relationship for IGA response after 16 weeks of treatment?
- What is the form of this dose-response?

• What doses deliver sufficient efficacy in terms of IGA response after 16 weeks of treatment?

Results from the interim analysis indicate that there is no dose-response relationship and therefore the second and third questions are no longer relevant. Thus the analysis of the primary variable will focus only on the logistic regression analysis described in the protocol, establishing the presence or absence of a dose-response relationship. The MCP-Mod procedure as outlined in the protocol will not be carried out.

The primary objective will be achieved if the null hypothesis of no difference between treatment groups is rejected at 5% one-sided level.

A logistic regression model will be fitted with IGA response as the outcome variable and treatment (dose as categorical variable) and baseline IGA as covariates.

The response  $Y_{ij}$  for subject j in dose group i receiving dose  $d_i$  is modelled as  $Y_{ij} \sim Bin(1, p_{ij})$  with  $p_{ij} = logit^{-1}(\delta_i + \mathbf{x}_{ij}; \boldsymbol{\beta}), i=1,..., 5, j=1,..., n_i$ 

where Bin(1,p) denotes the binomial distribution with parameter 1 and p,  $\delta_i$  is the effect of dose  $d_i$ ,  $\beta$  refers to the vector of regression coefficients corresponding to additional covariates  $x_{ij}$  which represent the baseline IGA category. Finally,  $n_i$  is the number of subjects allocated to each treatment group. If the covariate baseline IGA prevents fitting of a model, it will be dropped.

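### Wald p-values for IGA response are conservative at the planned 10% placebo rate: the four-degree-of-freedom treatment test runs at about 1% instead of 5% at the interim count of 187, before any Fisher fallback

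*SAP*

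**What the plan says.** - SAP 5.2.2, Logistic regression, on the test: "All p-values reported on linear hypotheses about regression coefficients will be based on the Wald tests from Type III analyses".
- SAP 2.5.2 drops MCP-Mod and leaves the logistic regression as the primary analysis, with "treatment (dose as categorical variable) and baseline IGA as covariates". Dose has five levels, so equality of all arms is a test on four degrees of freedom (df).
- SAP 2.5.2, success criterion: "The primary objective will be achieved if the null hypothesis of no difference between treatment groups is rejected at 5% one-sided level". SAP 2.1, general rule: "the level of significance will be set to 5" percent, two-sided.
- SAP 3, planning assumptions: "A placebo response rate of 10% was assumed", and "A maximum treatment effect for ZPL389 of 20%-points higher than placebo wass assumed". The allocation is 2:1:1:2:2.
- SAP 5.2.2 warns: "It should be noted that this model might not converge if response rates are too low". If the model does not converge, region is dropped, then baseline IGA, and then Fisher's exact test is used.
- SAP 5.2.3 pools only the odds ratio of a dose against placebo over 100 imputations. It shows no pooled four-df test.
- SAP 1.1 gives 187 as the number in the May 2020 interim analysis. SAP 3 says only that the final number is below 360.

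**The concern.** On the logit scale, the standard error of an arm's log odds grows faster than the log odds itself as responders become few. An arm with very low response therefore loses weight in the Wald statistic, and an arm with no responders adds almost nothing, even when it is the clearest sign of a difference. A 10% rate in arms of 23 to 47 patients implies about 2 to 5 expected responders per arm, which is where this happens.

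The SAP already expects to find no dose-response. If the actual size is a fraction of the stated 5%, a non-significant primary result is easier to obtain, and is weaker evidence of no effect, than a reader of the stated level would think.

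**Working it through.** **The plan's own figure.** SAP 3 gives 90% power at N=360 and one-sided 2.5% for the MCP-Mod test. Simulating that test with the seven candidate shapes of Protocol 9.4.2 gives a minimum power of 91.7% on the logit scale (critical value 2.32), so the planning inputs reproduce. The SAP gives no size or power for the Wald test that replaced it.

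**Inputs.** Placebo rate 10%, maximum 30% and allocation 2:1:1:2:2 (SAP 3). Splitting 187 in that ratio gives 47:23:23:47:47. The main calculations assume no missing data and no covariate.

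**Formulas**, with p_i the observed rate in arm i, p̄ the pooled rate, η_i = logit(p_i) and w_i = n_i p_i(1−p_i):

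- Wald: W = Σ w_i(η_i − η̄)², where η̄ is the w-weighted mean
- Score: S = Σ n_i(p_i − p̄)² / [p̄(1−p̄)]

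Both are compared with 9.488, the 95% point of chi-square on 4 df.

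**Mechanism, checkable by hand (illustrative counts).**

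- Responders 5, 2, 1, 14, 14 in arms of 47, 23, 23, 47, 47: p̄ = 36/187 = 0.1925.
  - S = 2.24 + 1.65 + 3.29 + 6.71 = 13.89.
  - W = 3.45 + 2.22 + 3.25 + 3.02 = 11.93 (unrounded terms). Both reject.
- Change the 10 mg arm from 1 responder to 0. The evidence is stronger and S rises to 16.40 (p=0.003). That arm's Wald weight goes to zero and W falls to 8.57 (p=0.07), so Wald no longer rejects.

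**Four-df test, no Fisher fallback** (200,000 simulated trials per cell; power is for 30 and 50 mg at the higher rate and the other arms at 10%):

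| N | Size, Wald / score | Power 10% v 30%, Wald / score | Power 10% v 20%, Wald / score |
|---|---|---|---|
| 187 | 1.0 / 4.6% | 64.6 / 79.4% | 11.3 / 25.8% |
| 240 | 1.6 / 4.6% | 84.2 / 90.0% | 21.6 / 34.3% |
| 300 | 2.1 / 4.7% | 94.3 / 96.1% | 34.5 / 44.5% |
| 360 | 2.6 / 4.9% | 97.9 / 98.5% | 45.6 / 52.9% |

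The loss at 10% v 30% is about 15, 6, 2 and 0.5 points. At 10% v 20% it is about 15, 13, 10 and 7.

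With baseline IGA in the model (assumed 40% severe, odds ratio 0.4; 3,000 trials, N=187), size is 1.0% Wald, 4.5% score and 6.7% likelihood ratio. Power for 10% v 30% is 65.8% Wald and 80.9% score.

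**Candidate shapes at N=187, with and without Fisher's test** (10% rising to at most 30%; 20,000 trials). In the Fisher column every data set with a zero-responder arm goes to the exact test:

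| Shape | Wald | Wald + Fisher | Score |
|---|---|---|---|
| null (size) | 1.1% | 3.8% | 4.7% |
| sigEmax1 | 50.5% | 60.6% | 67.9% |
| sigEmax2 | 45.5% | 55.4% | 62.8% |
| sigEmax3 | 47.9% | 48.6% | 59.9% |
| sigEmax4 | 57.6% | 63.6% | 71.3% |
| Emax1 | 44.7% | 47.5% | 56.8% |
| Emax2 | 44.2% | 48.7% | 57.3% |
| beta | 45.5% | 49.6% | 58.5% |

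The loss is 12-17 points without the fallback and about 7-11 with it. For the 10% v 30% pattern with baseline IGA in the model, a generous stand-in for the fallback gives 73.2% against 78.9%, a loss of 5.7 points. A zero-responder arm is expected in 1 − (1−0.9⁴⁷)³(1−0.9²³)² = 18.7% of null trials.

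**Pairwise tests against placebo, exact enumeration, two-sided 5%:**

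| Arms | Size at 10%, Wald / score | Power 30% v 10%, Wald / score |
|---|---|---|
| 47 v 47 | 2.1 / 5.9% | 68.0 / 70.5% |
| 23 v 47 | 2.0 / 3.8% | 53.4 / 57.4% |

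**Missing data.** A simplified imputation check with an assumed 15% missing gave the pooled score chi-square a size of 5.0% and power of 71.6%, against 48.1% for Wald.

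**The case against.** The strongest reply is that the large figures belong to one corner of the problem, and most of that stands.

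- A reader might infer that every logistic-regression p-value in the SAP runs at about 1% and loses 11 points or more. The documents do not support that. Those figures hold only for the four-df test near N=187 before the fallback. The comparisons actually coded in SAP 5.2.3 are pairwise and lose 2.5-4 points at 10% v 30%. At a one-sided 5% level their Wald size is 4.0% (47 v 47) and 4.3% (23 v 47), close to nominal.
- The count of 187 is the interim number. Patients still in the trial then also enter the full analysis set, so 187 is the small end of the range.
- SAP 5.2.2 has a fallback, and it would remove much of the size deficit. This stands only in part, because the trigger is non-convergence, which a zero-responder arm need not cause. With 8/47 against 0/47, a standard fitting routine reported convergence with a coefficient of −22, a standard error of 11,591 and Wald p=0.998. The score p is 0.003 and Fisher's p is 0.006. The pooling code in SAP 5.2.3 takes only an estimate and a standard error, so a Fisher p-value has no place in it.
- It is also tempting to extend the point to EASI50 and EASI75. The documents give no response rates for them. At an assumed 30% rate and N=187, four-df Wald size is about 4%, so no claim is made there.
- The decision to stop followed the interim results and not this p-value. SAP 2.6.7 also reports rate differences with intervals that do not use the logit Wald test.

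**Conclusion.** The point holds for IGA response, with limits. At the planned 10% placebo rate and N=187, the four-df Wald test has a size of about 1% where 5% is stated. It loses 12-17 points of power against a score test over the seven candidate shapes. If every zero-responder arm went to Fisher's test, size would be about 3.7% and the loss about 6-11 points, but the SAP does not ensure this. At N=240 to 360 the loss for 10% v 30% falls from about 6 to 0.5 points. For a smaller true effect (10% v 20%) it is still 7-13 points, and size stays below 3%.

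The error is conservative. A reader might take it as a threat to the type I error rate; it is not. The harm is that a non-significant result supports the absence of a dose-response less well than its stated level suggests.

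The figures rest on the 10% rate, an exact 2:1:1:2:2 split and, apart from one simplified check, no missing data. The final N is unknown.

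Separately, a four-df chi-square test has no direction, so the one-sided 5% in SAP 2.5.2 cannot be applied to it.

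**What to change.** In SAP 5.2.2, base the treatment p-values for IGA response (the overall four-df test and each dose against placebo) on the Rao score test in the logistic model. The Cochran-Mantel-Haenszel test stratified by baseline IGA matches it closely. In SAP 5.2.3, pool the score chi-square statistics over the 100 imputations with a standard rule for combining test statistics. Keep the logistic model for odds ratios and intervals. The score statistic exists when an arm has no responders, so the p-value no longer needs the Fisher step. The likelihood-ratio test is not a good substitute: its size at N=187 is 6.7%.

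In SAP 2.5.2, replace the one-sided level with one that fits the test, and reconcile it with the two-sided 5% in SAP 2.1.

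The cost is one changed sentence, a pooling rule and a few lines of code, with no new data. There are two downsides. The score p-value and the Wald odds-ratio interval can disagree near the threshold, and the pairwise score test can run slightly above nominal (5.9% at 47 v 47). Interim results were already known when the SAP was written, so the change should be recorded before final database lock. After lock, report the score test as a supplementary analysis.
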